1 **Title:** Decreasing Postoperative Pain Following Endometrial Ablation: A Randomized
2 Controlled Trial

3
4 **Principal Investigator:** [name]

5
6 **Sub-Investigator:** [name]

7
8 **Epidemiologist/Analyst:** [name]

9
10 **Purpose:** To determine whether paracervical injection of long acting local anesthesia
11 decreases postoperative pain following endometrial ablation under general anesthesia.

12
13 **Background:**

14 Destruction of the endometrial lining to control bothersome uterine bleeding
15 has been implemented since 1937 (ACOG Committee on Practice Bulletins, 2007).
16 Currently there are various different ‘second generation’ energy sources to avert such
17 bleeding, five of which are now approved in the United States (ACOG Committee on
18 Practice Bulletins, 2007). These 5 second generation devices include:
19 Thermachoice/Cavaterm, which use high temperature fluid within a balloon; Microsulis,
20 which applies microwaves; Novasure, which uses bipolar energy; Hydrothermablator,
21 which uses free fluid at high temperatures; ELITT, which uses laser thermotherapy; and
22 HerOption, which uses cryoablation. Patient selection for endometrial ablation is
23 crucial, as it is intended for premenopausal women with normal uterine cavities and no
24 desire for future fertility that are affected by heavy menstrual bleeding. Since the
25 introduction of the initial ‘second generation’ device in 1997 these modalities have
26 overtaken the industry mostly due to their ease of use and shorter operative times.
27 Regardless, a Cochrane review finds insufficient evidence to prove superiority of these
28 newer modalities over the traditional ‘gold standard’ resectoscopic technique (Anne
29 Lethaby, 2013).

30
31 Endometrial ablation has been demonstrated in a variety of settings including
32 outpatient surgical centers as well as physician’s offices. Evidence suggests that
33 microwave endometrial ablation under local anesthesia is a safe and acceptable practice
34 (Wallage S, 2003). Very often, when endometrial ablation is performed as an outpatient
35 procedure, patients are pre-medicated and then receive a paracervical injection of local
36 anesthesia to control pain intraoperatively (Mark H. Glasser, 2009). When endometrial
37 ablations are performed as an outpatient procedure through a surgical center, a variety
38 of anesthesia techniques are employed depending on the infrastructure and human and
39 institutional resources available. These techniques may vary from conscious sedation to
40 general anesthesia, all of which have been proven to be acceptable methods.

41
42 In this center endometrial ablations are performed as an outpatient procedure
43 under general anesthesia with a variety of induction techniques and intraoperative pain
44 management practices. According to physician preference, patients may receive an

45 additional paracervical injection of local anesthetic before the procedure, immediately
46 after, or not at all. To date, there are no studies evaluating the efficacy of local
47 anesthetic in addition to general anesthesia for patients receiving endometrial ablation
48 to guide physician practice. The purpose of this study is to evaluate the efficacy of local
49 anesthetic, in addition to general anesthesia, in our large, community-based patient
50 population, in meaningfully decreasing postoperative pain.

51
52

53 **Methods:**

54 This study will be a single center prospective single blind randomized controlled
55 trial of premenopausal women undergoing endometrial ablation. This study will take
56 place in the Christiana Hospital outpatient surgical center. Patients will include English
57 speaking premenopausal women aged 30 – 55 scheduled to undergo outpatient
58 endometrial ablation in the surgical center. These patients will be recruited either in
59 physician’s offices, by telephone based on surgical scheduling, or on the day of their
60 procedure. All consents will be signed in person.

61

62 **Study Design:**

63 Frequently, providers will give their patients additional analgesia in the form of a
64 local anesthetic injected as a paracervical block, either before or after the completion of
65 the procedure with the hope of reducing postoperative pain. This practice is not
66 standardized, as its efficacy has never been evaluated in the setting of endometrial
67 ablation under general anesthesia.

68

69 The purpose of this study is to assess the efficacy of this additional local
70 anesthesia upon completion of endometrial ablation under general anesthesia.
71 Patients, once consented, will be randomized in blocks of 6 to either the treatment
72 group or control groups. Those randomized to the treatment group will receive a
73 paracervical injection of 20 mL 0.25% Bupivacaine at the completion of the procedure
75 equal volume injection of normal saline with the same paracervical technique.
76 Paracervical injection will be standardized to include a total dose of 20 mL divided into
77 four 5 mL injections at the 2, 4, 8, and 10 o’clock positions on the cervix (Howard W.
78 Jones III, 2008). Paracervical block will be given at the completion of the endometrial
79 ablation.

80

81 Only the patients and PACU staff will be blinded to the injected solution. Once
82 general anesthesia has been induced the circulating nurse will open the study patient’s
83 unique randomization sequence and the appropriate study solution will be drawn in the
84 operating room. The endometrial ablation procedure will be performed by the surgeon
85 in accordance with that surgeon’s specific preference for technique and device. Upon
86 completion of the procedure, and before general anesthesia is reversed, the
87 paracervical injection of the patient’s unique study solution will be administered as
88 described above. The operating room team including the surgeon, anesthesiologist, and

[figure not shown]
89 ancillary staff will be aware of the injected solution's contents. The post anesthesia care
90 unit (PACU) staff responsible for assessing immediate and delayed postoperative pain
91 will not be aware of the contents of the injected solution, except when necessary for
92 any unexpected complication, in which case the pharmacist maintaining the
93 randomization coding will break the code for that particular patient. All patients will
94 receive IV Toradol with completion of the procedure and have a standardized rescue
95 analgesia protocol in place in the postoperative care unit setting in accordance with the
96 current practice described above. Per the nursing protocols postoperative pain will be
97 assessed using 10 point Visual Analog Scale (VAS) and if patient's pain is above or equal
98 to a 5, on the 10 point scale, they may receive additional analgesia in the form of
99 intravenous (IV) medication or by mouth tablets (PO). Pain scores, as well as rescue
100 analgesic administered, is routinely recorded by the nursing staff and converted to a
101 patient's electronic health record.

102

103 Due to the infrastructure set up, at CCHS outpatient endometrial ablations are
104 performed under general anesthesia with the patients asleep for the entire procedure.
105 Per the standard surgical center protocol postoperative patients will be assessed
106 regularly for postoperative pain. If the patients express pain equal to or beyond a
107 predetermined threshold of 5, on a visual analog pain scale from 0 through 10, they may
108 receive rescue analgesia. Patients are taken directly from the operating room to the
109 PACU where their pain is assessed on arrival by trained nursing staff. Patients are kept
110 in Phase 1 of recovery for a minimum of 30 minutes, and a minimum of 30 minutes in
111 Phase 2 before discharge following general anesthesia. At a minimum a postoperative
112 patient's pain is assessed every 10 minutes in Phase 1, and every 15 minutes in Phase 2.
113 Patients are candidates for rescue analgesic medications, generally in the form of
114 Dilaudid or Fentanyl, if their pain score is greater than 5 out of 10. In Phase 1 pain
115 medication is generally given in IV form whereas in Phase 2 pain medication is usually
116 given PO.

117

118 Figure 1: Visual Analog Scale

119

120

121 Upon discharge all patients will be given two additional 10 point VAS forms and
122 will be instructed to complete these two pain assessments at 4 hours and 8 hours after

123 their surgery. These pain scales will be labeled before discharge with the patient's study
124 identification code, date, the times they are to be completed, and instructions to retain
125 the forms until they have spoken with the study staff on the following day. Each patient
126 will be discharged with an additional prescription for twelve tablets of Tylenol #3. Each
127 patient will then be contacted on the day following their surgery by a study investigator
128 to record the patient's home pain scores as recalled by the patient by use of the two
129 pain scales completed at 4 hours and 8 hours postop. Each patient will also be asked to
130 disclose how many of the twelve Tylenol #3 tablets they have remaining.

131

132 **Primary Outcome:**

133 We propose to test a 40% decrease in the mean 10 point VAS postoperative pain score
134 at 1 hour after the operation. This percent decrease is based on a separate IRB
135 approved retrospective chart review of the most recent patients who underwent an
136 endometrial ablation at the Christiana Hospital surgical center. This retrospective chart
137 review found that of the last twenty patients who underwent an endometrial ablation,
138 without any additional local anesthesia in the form of a paracervical block, the mean
139 postoperative pain score at 1 hour was 2.85 ± 2.21 . The 40% hypothesized reduction in
140 pain is equivalent to approximately 1 full point on the VAS scale and felt to be a clinically
141 meaningful decrease at the lower end of the VAS scale that could influence policy and
142 practice. The average standard deviation between the mean 1 hour postoperative pain
143 scores between the reviewed charts of the 20 patients receiving a paracervical block
144 and the 20 that do not was 1.78, approximately equal to 75% of the average mean pain
145 scores for the 40 patients who did and did not receive a paracervical block. Using a two
146 tailed test, a Type I error of 5% and statistical power of 80%, and an average standard
147 deviation equal to 75% of the average VAS scores in both groups, the study requires a
148 sample of 36 patients per study group. Assuming a 15% attrition rate this study requires
149 42 patients per study arm (84 total participants). Enrollment in this study will occur for
150 10 months, or until the number of participants needed per study group is met,
151 whichever occurs first. This allows at least 2 months for data analysis and report
152 composition. Enrollment will be monitored by the Principal Investigator ([name])
153 monthly, to gauge when enrollment should stop. To ensure ongoing enrollment of
154 similar numbers of participants in each study group, randomization in blocks of 2 will be
155 used, so that for each 2 patients enrolled, 1 will be assigned to each study group.

156

157 **Secondary outcomes:** The study will also conduct descriptive analyses of the study
158 group differences in postoperative pain scores at 4 and 8 hours following surgery,
159 amount of rescue analgesia required postoperatively, but before discharge, time to
160 discharge, postoperative nausea/vomiting requiring medication, blood loss, and amount
161 of narcotic remaining at postoperative day one.

162

163 **Data Points:**

164 Covariates

165 - age

166 - race/ethnicity

- 167 - Insurance type
- 168 Mediating variables
- 169 - BMI (height/weight)
- 170 - Indication for surgery
- 171 - surgeon (anonymous code)
- 172 - type of ablation
- 173 - cervical dilation
- 174 - type and number of previous surgeries
- 175 - intra-operative complication incidence
- 176 Outcomes
- 177 - 1 hour postop VAS pain score (primary outcome)
- 178 - 4 and 8 hours postop VAS pain score (secondary outcomes)
- 179 - blood loss
- 180 - time to discharge
- 181 - type and amount of postop opioid given
- 182 -postop anti-emetics given
- 183 - postop complication incidence

184
185

186 **Inclusion criteria:** English speaking premenopausal women, aged 30 – 55, undergoing
187 outpatient endometrial ablation at the CCHS SurgiCenter for menorrhagia, abnormal
188 uterine bleeding, or thickened endometrium.

189

190 **Exclusion criteria:**

- 191 - Known malignancy
- 192 - Weight < 50 Kg
- 193 - Amide allergy
- 194 - History chronic pain
- 195 - Cardiac arrhythmia
- 196 - Dilaudid/codeine allergy
- 197 - History of opioid use
- 198 - Inability to take PO Opioids
- 199 - Uterine anomaly
- 200 - Previous ablation
- 201 - Concomitant laparoscopic surgery
- 202 - Primary language other than English

203

204 **Data analysis:** Continuous variables will be assessed using Student's t-tests and
205 categorical variables will be assessed using the chi-square tests with Fisher's exact
206 significance levels should there be fewer than 5 observations in any cell. Non-
207 parametric tests may be used to compare median values of continuous variables. Linear
208 and logistic regressions will be conducted on continuous and categorical outcomes, to
209 adjust for any unexpected differences in covariates and to describe mediation of effect.
210 All data will be maintained on a CCHS server accessible only to those members of the

211 research team. All information will be coded based on the patients unique study
212 number.

213

214 Works Cited

215 ACOG Committee on Practice Bulletins. (2007, May). *www.acog.org*. Retrieved 09 21,
216 2015, from [http://www.acog.org/Resources-And-Publications/Practice-](http://www.acog.org/Resources-And-Publications/Practice-Bulletins/Committee-on-Practice-Bulletins-Gynecology/Endometrial-Ablation)

217 [Bulletins/Committee-on-Practice-Bulletins-Gynecology/Endometrial-Ablation](http://www.acog.org/Resources-And-Publications/Practice-Bulletins/Committee-on-Practice-Bulletins-Gynecology/Endometrial-Ablation)

218 Anne Lethaby, J. P. (2013). *Endometrial resection and ablation techniques for heavy*
219 *menstrual bleeding* . Retrieved September 2015, from The Cochrane Library:

220 <http://www.thecochranelibrary.com>

221 Cohen, J. (1977). *Statistical power analysis for the behavioral sciences*. New York:

222 Academic press.

224 11). Philadelphia, PA: Wolters Kluwer.

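### As narrated, the allocation is opened before the ablation, so an unblinded operating room team can know the arm while giving analgesia that the study does not list for collection (optional, inexpensive improvement)

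*Combined protocol and SAP*

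**What the plan says.** The combined protocol and SAP sets out the order of steps in Study Design. Once "general anesthesia has been induced the circulating nurse will open the study" patient's "unique randomization sequence and the appropriate study solution will be drawn in the" "operating room. The endometrial ablation procedure will be performed by the surgeon", by that surgeon's preferred technique and device. The injection comes on "completion of the procedure, and before general anesthesia is reversed, the" team giving it at that point.

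On blinding, the same section states: "Only the patients and PACU staff will be blinded to the injected solution". It adds that the surgeon, the anesthesiologist and "ancillary staff will be aware of the injected" solution's contents. It does not say when they become aware.

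On analgesia, the Background says that ablations at this center are done "under general anesthesia with a variety of induction techniques and intraoperative pain" management practices. Study Design fixes three things: the paracervical injection, IV Toradol for everyone at completion, and a rescue protocol in the PACU. None of these governs analgesia during the case.

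On data, the Data Points list includes type of ablation, cervical dilation, intraoperative complications, blood loss, postoperative opioids and postoperative anti-emetics. It has no item for intraoperative analgesics. Routine recording is mentioned for pain scores and for the rescue "analgesic administered, is routinely recorded by the nursing staff and converted to a" electronic record.

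**The concern.** The solution is not needed until the ablation is over, yet as narrated the code is opened before the ablation starts. The people who choose the patient's analgesia during the case can therefore know whether bupivacaine or saline will follow. If they treated the arms differently because of that knowledge, and if analgesia given during the case still acts one hour after the operation, the difference would enter the primary comparison. The direction cannot be predicted. Extra analgesia for saline patients would hide an effect, and extra analgesia for bupivacaine patients would create or enlarge one.

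The plan's safeguards do not cover this route. Blinded patients and PACU nurses would score accurately a patient who had in fact been treated differently. Randomization balances varied practice in expectation, but not a response to the allocation that arises after it. With no data field, the study data could neither reveal nor rule out such a difference.

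**Working it through.** **1. Timeline.** Setting the Study Design statements in order:

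| Step | Can the operating room team know the arm? |
|---|---|
| Induction | Not from opening the code, which comes later (but see step 5) |
| Code opened, solution drawn in the operating room | Yes, from here on |
| Ablation | Yes |
| Injection on completion | Yes; first time the solution is needed |
| Anesthesia reversed, transfer to PACU | PACU staff blinded |

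The placing of the ablation after the opening rests on the order of narration. The text gives only an earliest time for opening. Moving the opening to after the ablation removes the ablation from the period in which the opened code can reveal the arm.

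**2. The plan's own sample size.** Inputs from Primary Outcome: control mean 2.85, reduction 40%, SD equal to 75% of the average of the two means, two-sided 5%, power 80%.
- Difference: 0.40 × 2.85 = 1.14. Treated mean: 2.85 − 1.14 = 1.71.
- SD: 0.75 × (2.85 + 1.71)/2 = 1.71.
- n per arm: 2 × (1.960 + 0.842)² × 1.71² / 1.14² = 35.3, so 36. This reproduces the stated 36.

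The point does not alter this number.

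**3. What a shift would do (illustration).** The documents give no size for any bias. Assume shift = (between-arm difference in the share given extra analgesia) × (effect of that analgesia on the 1-hour score). If that effect were as large as the planned 1.14 points:
- a 10-point difference in share gives 0.10 × 1.14 = 0.114
- a 20-point difference gives 0.20 × 1.14 = 0.228

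At half that effect (0.57), the shifts are 0.057 and 0.114.

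The standard error is 1.71 × √(2/36) = 0.403. Power and false-positive rate come from the noncentral t distribution with 70 degrees of freedom. The noncentrality is (1.14 − shift)/0.403 for power against a true effect, and shift/0.403 when there is none.

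| Shift | Power, shift against treatment | False positives, no true effect |
|---|---|---|
| 0 | 80% | 5.0% |
| 0.114 | 71% | 5.9% |
| 0.228 | 61% | 8.6% |

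With the SD of 2.21 that the chart review gives for patients without a block, the standard error is 2.21 × √(2/36) = 0.521. The same shifts then take power from 58% to 49% or 41%, and false positives from 5% to 5.5% or 7.2%.

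**4. What a by-arm report could show.** With 36 per arm, the 95% half-width for a difference in shares is at most 1.96 × √(2 × 0.25/36) = 0.23, or 23 percentage points. For an amount it is 1.994 × √(2/36) = 0.47 SD. A large imbalance would show. One of 10 to 20 points could be missed.

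**5. Predictability before opening.** Study Design gives blocks of 6, and Primary Outcome gives blocks of 2. With k patients per arm in a block, someone who knows the block size and every earlier allocation can deduce on average 2k/(k + 1) of the block's 2k patients.
- Blocks of 2 (k = 1): 1 of 2, or 50%.
- Blocks of 6 (k = 3): 1.5 of 6, or 25%.

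This assumes that the same unblinded staff follow consecutive study patients, which the documents do not say. Opening the code after induction therefore does not guarantee concealment up to that moment.

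**The case against.** The strongest reply is that nothing here is hidden or shown to do harm. The trial is declared single blind and says who is blinded. Outcome assessment is well protected by an equal-volume saline injection, blinded patients and PACU staff, Toradol for all and a PACU rescue protocol. No statement suggests that the team would treat the arms differently, and persistence of intraoperative analgesia to one hour is an assumption. The sentence on varied practice stands in the Background and describes usual care. Intraoperative drugs may well be held in routine anesthesia records. All of this stands, and it is why the point is graded as optional.

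What the reply does not answer is narrower. A single-blind design does not require the code to be opened before the ablation. Nothing in Methods restricts the varied practice for the trial. A routine record that the plan does not list for collection is not part of the planned study data.

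A reader might infer more than the documents support, in either direction:
- **That the primary comparison is biased.** Varied practice alone is not bias, and no differential treatment is documented.
- **That only analgesia given after the code is opened is exposed.** With small blocks and an unblinded team, some allocations may be predictable earlier.
- **That only a very large imbalance could matter.** The table above shows loss of power and excess false positives at modest shifts.
- **That moving the opening step is worth more than recording the analgesia.** The documents do not say when in the case analgesia is given, so the two cannot be ranked.
- **That the Background remark on physician preference shows varied systemic analgesia.** It concerns the paracervical injection, which the protocol fixes.

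**Conclusion.** The point holds as a low-severity, optional improvement, not as an error in the plan. The order of steps as narrated lets an unblinded team know the arm during the ablation, and the listed data could not show whether intraoperative analgesia differed by arm. Whether that ever happens is unknown, and so is the size of any effect.

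The figures of 71% and 61% power, and 5.9% and 8.6% false positives, rest on assumed shifts of 0.11 and 0.23 points and on the plan's own SD and sample size. They show what such shifts would do and are not estimates of bias. The conclusion also rests on reading the narrated order as the intended order.

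**What to change.** 1. In Study Design, state that the circulating nurse opens the code and draws the solution only after the ablation is complete, just before the injection.
2. Add intraoperative analgesic type and amount to the Data Points. Report it by arm with a 95% confidence interval as a check on co-intervention. It should not be an adjustment covariate for the primary effect, because it arises after randomization. The Data analysis section plans regressions on covariates and for mediation, so label the new field clearly to keep it out of the primary adjustment.

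**Cost.** A wording change, one more data field, and a short delay before anesthesia is reversed while the solution is drawn. The sample size and the single-blind design are unchanged.

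**Limits.** Item 1 leaves the interval from injection to reversal exposed. It also does not protect patients whose arm an unblinded team can predict from the block size. The blocks of 6 in Study Design and the blocks of 2 in Primary Outcome must be reconciled in any case. Item 2 can miss a moderate imbalance at this sample size.

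### The protocol gives two block sizes for the same randomization, 6 and 2; the blocks-of-2 version would let a fully informed observer know 42 of 84 allocations in advance

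*Combined protocol and SAP*

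**What the plan says.** The Study Design section states: "Patients, once consented, will be randomized in blocks of 6 to either the treatment" group or control. The last sentence of the Primary Outcome section gives a different rule, with balance as its reason: to keep "similar numbers of participants in each study group, randomization in blocks of 2 will be" "used, so that for each 2 patients enrolled, 1 will be assigned to each study group". No strata, phases or subgroups are described to which the two sizes could separately apply, and neither sentence is marked as superseded.

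Other provisions that bear on the point:

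- **Blinding (Study Design).** "Only the patients and PACU staff will be blinded to the injected solution". The surgeon, the anesthesiologist and the rest of the operating team know what was injected.
- **Opening the assignment (Study Design).** The circulating nurse opens it only after induction, and a pharmacist maintains the code.
- **Recruitment (Methods).** Patients may be recruited in offices, by telephone from the surgical schedule, or on the day of surgery.
- **Size (Primary Outcome).** 36 per group, raised to 42 per arm (84 in total) for 15% attrition. Enrollment ends at 10 months if that comes first.

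**The concern.** A list generator cannot follow both sentences. Each defines a usable 1:1 list by itself, and 84 is divisible by both 6 and 2; the defect is that there are two. A later reader could not tell which scheme was planned.

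The two schemes also differ in how well the next assignment can be predicted. In a block of 2 the first allocation fixes the second. Because the operating team learns each allocation, anyone who also knows the block size knows the second patient's arm as soon as the first is treated. Opening the assignment after induction keeps the current patient's assignment sealed, but does not prevent inference from the previous case. If that knowledge reached someone who recruits, the next patient could be approached or deferred according to expected pain, mainly with day-of-surgery recruitment. The planned regression adjusts for measured covariates and cannot be relied on to remove selection on unmeasured pain risk.

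**Working it through.** **1. The plan's sample size.** From the Primary Outcome section: control mean 2.85 and a 40% reduction, so the difference is 0.40 × 2.85 = 1.14 and the treated mean is 1.71. The average mean is (2.85 + 1.71)/2 = 2.28, and the SD is 0.75 × 2.28 = 1.71. The normal approximation at two-sided 5% and 80% power gives 36 per group, as stated. For attrition, 36 × 1.15 = 41.4, which rounds up to the stated 42; 36/0.85 = 42.4 would round up to 43. The total of 84 is accepted here. Block size plays no part in this calculation.

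**2. Allocations known with certainty.** Assume no stratification (none is stated) and an observer who knows the block size and every earlier allocation. An allocation is certain once one arm is used up within the block.

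- Blocks of 2: 84/2 = 42 blocks with exactly one certain allocation each, so 42 of 84 (50%).
- Blocks of 6: 20 possible orders, of which 12 have one certain allocation, 6 have two and 2 have three. The mean is (12×1 + 6×2 + 2×3)/20 = 1.5. Over 14 blocks that is 21 of 84 (25%), with a range of 14 to 42.

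**3. Best guesses.** The observer guesses the arm with fewer patients so far and tosses a coin at ties. Blocks of 2: 1.5 of 2 correct, 75% (63.0 of 84). Blocks of 6: 4.1 of 6 correct, 68.3% (57.4 of 84). This guess does not require knowing the block size.

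**4. An alternative list.** Six blocks of 6 and six of 8 in random order end exactly at 6×6 + 6×8 = 84. By simulation (2,500 lists; the observer knows the composition but not the order), 5.3 of 84 allocations are certain (6.3%) and 67.4% of guesses are correct.

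**5. What steering could do (illustration only).** Suppose every non-tied guess is acted on, moving the enrolled patient's expected 1-hour score by d points, up or down according to the arm guessed. With g the correct-guess rate, the shift in the group difference is 2d(2g − 1). SD 1.78 (Primary Outcome) and 36 per arm give SE = 1.78 × √(2/36) = 0.420 on 70 df. Type I error is from the noncentral t, two-sided 5%.

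| Scheme | Shift | d = 0.5 | d = 0.25 | d = 0.5, acted on in a quarter of blocks |
|---|---|---|---|---|
| Blocks of 2 | 1.00d | 0.217 | 0.090 | 0.060 |
| Blocks of 6 | 0.73d | 0.138 | 0.072 | 0.055 |
| Six of 6 and six of 8 | 0.70d | 0.129 | 0.069 | 0.055 |

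The documents give neither d nor the share of blocks acted on.

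**6. Is the balance aim met without blocks of 2?** The running imbalance never exceeds 1 patient with blocks of 2, 3 with blocks of 6 and 4 with the 6/8 list. Fixed blocks of 6 and the 6/8 list are both exactly balanced at 84. Power for 1.14 points at SD 1.78 is 82.65% at 42 v 42 and 82.57% at 44 v 40. If enrollment stops at 81, it is 81.19% at 42 v 39 against 81.24% for an equal split. Each loss is under 0.1 percentage point. These figures assume no attrition and serve only for comparison; at 36 per arm and SD 1.78, power is 76.4%.

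**The case against.** The contradiction is not in dispute. The case on the other side concerns the predictability argument and how far the remedy should go.

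- **The 42 of 84 needs a strong observer.** That person must know the block size, see every earlier allocation and be able to act before the next patient is approached. The documents do not say that operating staff recruit, nor whether list order follows consent or surgery. A patient whose list position was fixed before the previous case could not have been selected on it. The surgeon code under Data Points suggests several surgeons. If m surgeons shared cases equally and at random and saw only their own, about 42/m pairs would be exposed: 21, 10.5 and about 5 for m = 2, 4 and 8. This stands, and is why 42 is an upper bound.
- **The steering figures have no documentary basis.** At d = 0.5, patients steered toward opposite arms differ by a full VAS point, close to the hypothesized 1.14. At the mildest setting the two schemes differ only by 0.060 against 0.055. This also stands; the figures are illustrative.
- **Aligning both sections on blocks of 2 would equally remove the contradiction.** True. It would keep the more predictable scheme for an imbalance advantage that costs under 0.1 point of power to give up, and blocks of 6 are already in the protocol.
- **Varying sizes gain little in guess rate over fixed 6** (67.4% against 68.3%). True; the gain is in certain allocations, 5.3 against 21. Varying sizes are therefore recommended, not required.

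**Conclusion.** The concern holds. The protocol specifies two incompatible block sizes for one unstratified trial of 84, and this must be fixed before the list is generated. That conclusion rests on the text alone and needs no assumption about staff behavior.

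The predictability difference is real but conditional. For a fully informed observer, blocks of 2 make 42 of 84 allocations certain, against an expected 21 with blocks of 6. Correct guesses fall only from 75% to 68.3%. At equal knowledge, leaving blocks of 2 removes about 27% (fixed 6) to 30% (the 6/8 list) of any steering shift; the rest depends on concealment. Blinded PACU assessment, opening after induction and a pharmacist-held code limit the harm without stopping prediction within a pair. Nothing here shows that allocations were or would be subverted.

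**What to change.** **Required.** Delete the blocks-of-2 sentence from Primary Outcome and state one scheme, in identical words, in Study Design and Primary Outcome, with blocks larger than 2. The existing blocks of 6 would suffice.

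**Recommended.**

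- Use randomly varying sizes, for example six blocks of 6 and six of 8 in random order, ending at 42 v 42.
- Have the protocol say only that allocation is 1:1 in permuted blocks of varying size. Keep the sizes in the file of the pharmacist who maintains the code, withheld from recruiters, surgeons and operating staff.
- Assign numbers in strict sequence after consent and confirmed eligibility.
- Keep the running record of allocations from those who recruit, because guessing the arm with fewer patients needs no knowledge of block size.

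**Cost.** Protocol wording and list generation before the first patient. The sample size and planned test are unchanged.
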